3.0 Inclusion/Exclusion Criteria

Inclusion criteria

- Men and women with a stable symptomatic claudication for ≥ 6 months
- Ankle brachial index < 0.9

Exclusion criteria

- Uncontrolled Diabetes (HbA1C > 8.5 measured within 3 months prior to date of consent)
- Heart Failure
- COPD
- Critical limb ischemia (ischemic rest pain or ischemia-related non healing wounds or tissue loss)
- Prior amputation
- Exercise-limiting comorbidity (i.e., angina, chronic lung disease, or arthritis)
- Recent (<3 months) infrainguinal revascularization (surgery or endovascular revascularization) or revascularization planned during study period.
- Plans to change medical therapy during the duration of the study
- Active cancer
- Chronic kidney disease (eGFR <30 by MDRD or Mayo or Cockcroft-Gault formula).
- HIV positive, active HBV or HCV disease.
- Presence of any clinical condition that in the opinion of the principal investigator makes the patient not suitable to participate in the trial.
- Peripheral neuropathy, numbness, or paresthesia in the legs.
- Morbid obesity BMI > 36 or unable to fit into water-circulating pants.
- Open wounds or ulcers on the extremity.

As this study involves MR imaging, patients that have contraindications to MRI will be included in the study but will not be allowed to participate in the MRI procedure. Information about biomedical devices that may pose a risk to patients undergoing MRI is available on the Internet at www.MRIsafety.com. These exclusions include:

- Cardiac pacemaker
- Implanted cardiac defibrillator
- Aneurysm clips
- Carotid artery vascular clamp
- Neurostimulator
- Insulin or infusion pump
- Implanted drug infusion device
- Bone growth/fusion stimulator
- Cochlear, otologic, or ear implant
- History of claustrophobia or who are unable to lie flat or who do not fit inside the bore of the scanner

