1	
 1) Medical History and Physical Examination 2) Quality of life assessment 3) Measurement of ankle-brachial index 4) Familiarization with the 6-min walking test 	CTSI's Clinical Research Center at Goodman Hall	2 hrs
2	
 1) Leg MRI (reactive hyperemia) 2) Catheter placement and venous blood draw 3) Measurement of ankle-brachial index 4) Assessment of cutaneous vascular function 5) 6-min walking test 	Imaging Research Facilities and CTSI's Clinical Research Center at Goodman Hall	4 hrs

Table 1: Procedures involved, location and estimated duration of visits 1 and 2.

After the baseline assessment is complete, subjects will be randomly allocated to one of two groups using a random allocation software. Participants will be asked to

attend **3 treatments sessions/week for 6 consecutive weeks**. These sessions will be conducted at the CTSI’s Clinical Research Center at Goodman Hall and will last approximately 110 min. A research coordinator will supervise the patients during the sessions. On each session, subjects will initially have their body weight and blood pressure measured and recorded. Next, patients will be asked to change into the water-circulating pants (Figure 3) and lay in semi-recumbent position. The garments will be connected to the water pump and the treatment will be applied for 90 min. In the high-heat group, hot water will be circulated through the garment with the goal of increasing skin temperature to 40°C, while thermoneutral water (33°C) will be used in the low-heat group. Subjects will be allowed to drink water ad libitum during the sessions but will not be allowed to consume food. At the end of the session, body weight and blood pressure will once again be recorded. The research coordinator will measure temperature (sublingual measurements) and blood pressure every 15 minutes during the treatment and will also inspect the skin in the legs to look for potential signs of injury or adverse reactions to the treatment. The subject will be asked to complete a heat sensation scale every 15 minutes during the treatment. The research coordinator will clean the garment after each use using a hospital-grade disinfectant spray. The garment will also be washed in a washing machine every week.

Figure 3: Water-circulating garment system for thermotherapy application

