Leg thermotherapy for intermittent claudication

NCT02770547

Document Version: 12/11/2019

Statistical Analysis Plan

Demographic and clinical characteristics were summarized overall and by group. Two-sample tests, Wilcoxon Rank Sum test, Chi-square tests, or Fisher's Exact tests were used to compare the two groups. For the analysis of MRI-derived indices, absolute values were used for peak flow and flow per minute as sometimes the values reported from the machine were negative. Percentage change in peak flow is defined as $(\text{max absolute value} - \text{mean baseline absolute value}) / \text{mean baseline absolute value}$. For the outcome of 6-min walk test, the best of V1 and V2 was used as baseline. For the MRI-derived indices, the blood parameters, cutaneous microvascular function, and the experimental blood pressure, V2 was used as the baseline; while for the quality of life, V1 was used as the baseline. For physiological variables of systolic blood pressure, diastolic blood pressure, mean arterial pressure, heart rate, and temperature in the ear, change from baseline at each time point using the mean of total 18 sessions in two groups was plotted. Area under the curve (AUC), expressed as arbitrary units, for the total 90 minutes was plotted. The AUC for the change from baseline was also plotted in each session in each group. For the cutaneous microvascular function, mean arterial pressure, cutaneous vascular conductance (CVC) and MaxCVC were plotted by mean with standard error at each time point in each experimental visit; AUC for the total 14 time points were also plotted. In the experimental blood pressure, means with standard error were plotted for the change of systolic blood pressure, diastolic blood pressure and mean arterial pressure from baseline timepoint in high-heat therapy group or low-heat therapy group separately; change of AUC in systolic blood pressure, diastolic blood pressure and mean arterial pressure from baseline visit V2 were also plotted. For 6-min walk test, MRI-derived indices, blood parameters, quality of life, the AUC of cutaneous microvascular function indices, and AUC of experimental blood pressure, analyses were done with two different model types. First, linear mixed models with fixed effects for visiting time (V1 or V2, V3, V4) and intervention (high heat, low heat) were fit using the raw data. A significant interaction of time and intervention would indicate that there were differential effects of high and low heat over time. If the interaction was not significant, it was removed. In the main effects only model, a significant main effect for intervention would indicate that the two intervention groups are different (with the same magnitude of difference) across all time points (including baseline). Second, the changes from baseline to V3 and baseline to V4 were modeled with a linear mixed model. Here a significant interaction of time and intervention would mean the intervention effect was different at V3 vs V4. If the interaction was not significant, it was removed. In the main effects only model for change, a significant main effect for intervention would mean that there was an intervention effect, and it was of the same magnitude at V3 and V4. As the results were largely consistent, the results section focuses on the change score model results. Two sample t-tests were used to check whether the AUC for the change of physiological variables were different between two treatment groups. For the cutaneous microvascular function, the MaxCVC from two laser Doppler probes were compared at each timepoint using the linear mixed model with fixed effects for time point and probe, a significant interaction of timepoint and probe would indicate that the MaxCVC from two probes are different over time. The probe effects at each time point were also tested when the probe by time interaction was statistically significant at the significance level 0.05, or the main effects of probe were checked if the probe by time interaction was not statistically significant at the significance level 0.05. All analyses were performed using SAS v9.4.

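### Neither mixed model, as described, adjusts for the baseline value; the change-score analysis is valid, but adding baseline would cost almost nothing and could gain some precision

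*SAP*

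**What the plan says.** The SAP sets a baseline for each modelled outcome family. For the 6-min walk, "the best of V1 and V2 was used as baseline". V2 serves for the MRI, blood, cutaneous and experimental blood pressure outcomes, and V1 for quality of life. Section 5.0 of the protocol places these measurements before allocation: "After the baseline assessment is complete, subjects will be randomly allocated to one of two groups using a random allocation software".

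Two model types are then described.

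- **Raw data:** "linear mixed models with fixed effects for visiting time (V1 or V2, V3, V4) and intervention (high heat, low heat". Baseline is a level of the time factor, so it is part of the response. Once the interaction is dropped, the intervention effect is a group difference "across all time points (including baseline".
- **Change scores:** "Second, the changes from baseline to V3 and baseline to V4 were modeled with a linear mixed model". The SAP explains only the visit-by-intervention interaction and the intervention main effect: "In the main effects only model for change, a significant main effect for intervention would mean that there was an intervention effect". It does not list the fixed effects in full.

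The SAP reports that the two sets of results were largely consistent and that "the results section focuses on the change score model results".

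Section 8.0 of the protocol bases the sample size on the between-group difference in change in 6-min walk distance at 6 weeks, with no baseline adjustment.

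**The concern.** Baseline is a legitimate covariate here because it is measured before allocation and usually predicts follow-up. A change-score model subtracts all of it, which amounts to fixing the regression slope of follow-up on baseline at 1. If the true slope is below 1, a group that starts higher by chance tends to show a smaller change. A share of the imbalance equal to 1 minus the slope then enters the treatment estimate with reversed sign, and variance that baseline could explain stays in the residual.

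The agreement between the two model types is no check on this. With complete data, free baseline means and the interaction retained, the raw-data model gives essentially the same contrast as the change-score model. With the interaction removed, its group effect averages over baseline as well.

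At stake is some precision in a trial of 32 patients, and an estimate that does not depend on which group happened to start higher. Type I error is not at stake.

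**Working it through.** **Inputs from the protocol, section 8.0:** difference 50 m; SD of change 48.69 m (called a variance, but given in metres and used as an SD); 16 per group; power 0.802.

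**Assumed:** two-sided alpha 0.05 (section 8.0 states none); normally distributed 6-min walk tests, each with SD *s* and the same pairwise correlation rho; SD of single-visit change held at 48.69 m. Neither document gives rho or a baseline SD, so rho is taken from 0.5 to 0.9.

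**1. The plan's own figure.** SE of the change-score difference = 48.69 × √(2/16) = 17.21 m. The noncentral t distribution with 30 df gives power 0.8025 for 50 m, which reproduces 0.802.

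**2. Best-of-two baseline.** With B the larger of V1 and V2:

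- Var(B) = s²[1 − (1−rho)/π]
- Cov(B, follow-up) = rho·s²
- Var(change) = s²(1−rho)(2 − 1/π), set equal to 48.69², which gives *s*
- slope = rho / [1 − (1−rho)/π]
- residual variance after adjustment = s²{1 − rho²/[1 − (1−rho)/π]}

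Estimating the slope inflates the variance by 1 + 1/28 on average, so adjusted SE = residual SD × √[(2/16)(1 + 1/28)], with 29 residual df. A baseline imbalance of 1 SD of its sampling distribution shifts the change-score estimate by (1 − slope) × SD(B) × √(2/16).

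**3. 6-min walk, one visit** (change-score SE 17.21 m, power 0.802):

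| rho | s (m) | slope | adjusted SE (m) | SE difference | adjusted power | shift from 1-SD imbalance (m) | shift as % of 50 m |
|---|---|---|---|---|---|---|---|
| 0.5 | 53 | 0.595 | 16.02 | -7.0% | 0.855 | 7.0 | 14% |
| 0.7 | 69 | 0.774 | 16.70 | -3.0% | 0.825 | 5.2 | 10% |
| 0.8 | 84 | 0.854 | 16.99 | -1.3% | 0.812 | 4.2 | 8% |
| 0.9 | 119 | 0.930 | 17.27 | +0.3% | 0.799 | 2.9 | 6% |

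The share of an imbalance that enters the change-score estimate is therefore about 41%, 23%, 15% and 7%. Break-even in SE is at rho 0.88. At rho 0.95 the adjusted SE is 17.40 m (about +1%) and power is 0.793. A simulation of 100,000 trials under the same assumptions agreed: adjusted power was 0.857, 0.825, 0.811 and 0.799, and type I error was 0.049 to 0.051 for both models.

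**4. V3 and V4 pooled**, as in the SAP's main-effects change model. The follow-up mean has variance s²(1+rho)/2. The change-score SE is 14.43 m; the adjusted SE is 12.85, 13.69, 14.06 and 14.38 m, a difference of -10.9%, -5.1%, -2.6% and -0.3%. Break-even is at rho 0.91.

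**5. Upper limit on the loss.** Residual variance cannot exceed the variance of change, so the SE ratio is at most √[1 + 1/(2n−4)] for n per group. This gives 1.018 at n = 16, 1.025 at 12 and 1.041 at 8.

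**6. Outcomes with a single baseline visit** (equal SDs assumed). Break-even rho = 2(2n−4)/(2n−3) − 1 = 0.93 at n = 16, 0.90 at 12 and 0.85 at 8. The smaller values of n are illustrative for MRI, because section 3.0 of the protocol says that "patients that have contraindications to MRI will be included in the study but will not be allowed to participate in the MRI procedure". At rho 0.5 and n = 16, the net variance ratio is (1+0.5)/2 × 29/28 = 0.777, about 22% less variance.

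**The case against.** The case against acting is substantial.

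- **There is no error.** Both estimators are unbiased in a randomised trial, and the change score is the quantity the trial was sized on. This stands, and it is why the point is only one of efficiency.
- **The gain depends on an unstated rho.** For 6-min walk at one visit, rho 0.8 buys one point of power and rho 0.9 loses a fraction of a point. This also stands. Only at lower correlations is the gain visible.
- **Imbalance and precision are one benefit seen twice.** At rho 0.5, the adjusted SE before the slope cost and the shift combine as 15.74² + 6.98² = 17.21². The shift is already inside the change-score SE, and the confidence interval covers it on average over randomisations. The metre shifts describe a given unlucky allocation and must not be added to the SE gain. Likewise, a baseline difference of at least 1 SD of its sampling distribution occurs in about 32% of randomisations at any sample size.
- **The figures are model-dependent.** V1 is a familiarisation test, so V1 and V2 may not be exchangeable. With a single equal-variance baseline, adjusted power is 0.890 at rho 0.5 and 0.828 at 0.8, with break-even at 0.93. That alternative favours adjustment more.
- **The omission is inferred.** The change model's fixed effects are not fully listed, so an unmentioned baseline term cannot be ruled out.
- **The SAP is in the past tense.** A third model type chosen after results are known adds analytic flexibility. This is a real cost. It is contained by keeping the existing results and labelling the new ones.

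These points limit the size of the concern. They do not supply a baseline term that the SAP fails to describe, and the possible loss from adding one remains small.

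**Conclusion.** The concern holds as a small efficiency point. Neither model, as described, conditions on the baseline value. The change-score results remain valid and the planned power of 0.802 stands.

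Under the stated assumptions, adjustment would lower the 6-min walk SE by 1% to 7% at one visit, and by 3% to 11% with V3 and V4 pooled, for rho between 0.5 and 0.8. At rho 0.9 the two analyses are practically equal. For MRI, blood, cutaneous and quality-of-life outcomes, neither rho nor the analysed number is given. The gain there could be moderate if rho is low.

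The balance favours adjustment because the possible loss is bounded: at most 1.8% in expected SE at 16 per group, whatever rho or the ratio of SDs. Confidence is medium, because the omission is inferred from an incomplete model description and rho is unknown.

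**What to change.** In the V3/V4 change model, add the baseline value of the same outcome and its interaction with visit as fixed effects. Report the adjusted high-heat minus low-heat differences with confidence intervals beside the existing change-score results, without replacing them. If results were known when the adjusted model was added, label it post hoc. If baseline was already a covariate, the only change needed is to list it among the fixed effects.

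The cost is one or two model degrees of freedom per outcome and a rerun of the existing SAS models, with no new data. It also adds a third analysis that may differ from the first two, which the label should make plain. For outcomes with fewer patients, such as MRI, the bound on precision loss is somewhat larger: 2.5% at 12 per group and 4.1% at 8.

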Outcome measurements will be repeated after 9 sessions (3 weeks) and at the end of the treatment period (18 sessions). The protocol for these visits will be similar to visit 2, with the addition of quality of life assessment. The procedures involved are detailed on table 2. This visit is expected to last approximately 4.5 hrs. Subjects will be asked to fast overnight prior to attending this session but will be permitted to take their usual morning medication regimen.

Visit #	Procedures	Location	Duration
3 and 4	1) Leg MRI (reactive hyperemia) 2) Catheter placement and venous blood draw 3) Measurement of ankle-brachial index 4) Quality of life assessment 5) Assessment of cutaneous vascular function 6) 6-min walking test	Imaging Research Facilities and CTSI’s Clinical Research Center at Goodman Hall	4.5 hrs

Table 2: Procedures involved, location and estimated duration of visits 3 and 4.

Outcome Measures:

Reactive Hyperemia in the Popliteal Artery: Blood flow in the popliteal artery of the most symptomatic leg will be measured using MRI. We employed this technique in our initial study (IRB Protocol #1409063619). After the knee coil and the occlusion cuff are positioned on the most symptomatic leg, participants will be allowed to rest quietly for 15 min. Resting leg blood flow measurements and brachial systolic blood pressures will be completed every 5 min during this period. Next, a blood pressure cuff firmly wrapped around the lower thigh will be inflated to 75 mmHg above systolic blood pressure, or 250 mmHg, whichever is lower, for 5 min (8). Hyperemic flow will be measured for 10 min after cuff deflation. Flow reserve will be defined as the absolute difference between maximum hyperemic flow after cuff release and resting flow (9).

Cutaneous Microvascular Function: Laser-Doppler flowmetry probes, seated in the center of local skin heaters (Moor Instruments, UK), will be used to measure red blood cell flux, an index of skin blood flow (SkBF). Baseline SkBF will be recorded for 10 min after which local skin temperature will be increased to 39°C (0.1°C/s) and maintained at this level until a plateau is achieved (~40 min). Next, the local skin temperature will be elevated to 43°C, to induce maximal vasodilation. Cutaneous vascular conductance (CVC) will be calculated as laser-Doppler flux divided by mean arterial pressure (MAP), measured throughout the study via brachial artery oscillation, and normalized to maximal vasodilation (%CVC_{max}) (10, 11).

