8.0 Statistical Considerations

Sample size was estimated based on the ability to detect a significant change in 6-min walk distance from baseline to 6 weeks in the TT-treated group as compared to the control group. The studies of McDermott and co-workers (5) and Gardner and co-workers (2), which investigated the impact of home-based exercise training on walking tolerance in patients with IC, were used as a reference for the sample size calculations. We estimated the variance of improved walk distance by the MSE of Table 3 in the study of Gardner et al (2), which is 48.69 meters. Since both studies reported a non-significant change in 6-min walk in the attention-control group (95% confidence interval for McDermott's study is (-25.4 to 3.2) and for Gardner's study is (-6.33 to 14.33)), we predict that the change in 6-min walk in the control group, in our study, will be negligible (0). As pointed out by Perera et al (6), a change of 50 meters in the 6-min walk test is considered substantial and clinically meaningful in elderly subjects. Using this effect size $(50-0)/48.69$, we determined that **16 subjects per group** are needed to detect a substantial improvement by TT therapy with a power of 0.802.

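### The SAP names no high- versus low-heat comparison of 6-minute walk change at 6 weeks, although the trial was sized on that comparison

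*SAP*

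**What the plan says.** Protocol section 8.0 ties the sample size to one comparison: "Sample size was estimated based on the ability to detect a significant change in 6-min walk distance from baseline to 6 weeks", high heat against control. It assumes 50 m against 0 m, uses 48.69 m as the standard deviation, and arrives at 16 per group with power 0.802.

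Protocol section 5.0 fixes the follow-up visits: "Outcome measurements will be repeated after 9 sessions (3 weeks) and at the end of the treatment period (18 sessions". V3 is therefore 3 weeks and V4 is 6 weeks.

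The SAP analyses walk distance with two linear mixed models, each with two possible outputs:

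- **Raw data, interaction significant:** "A significant interaction of time and intervention would indicate that there were differential effects of high and low heat over time".
- **Raw data, interaction removed:** the main effect would mean "the two intervention groups are different (with the same magnitude of difference) across all time points (including baseline".
- **Change scores, interaction significant:** "Here a significant interaction of time and intervention would mean the intervention effect was different at V3 vs V4".
- **Change scores, interaction removed:** "In the main effects only model for change, a significant main effect for intervention would mean that there was an intervention effect". The SAP takes this single effect as common to the two follow-up visits, in the words "it was of the same magnitude at V3 and V4".

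The SAP says that its results section concentrates on the change-score model. For the comparison of the two laser Doppler probes it does give a next step: "The probe effects at each time point were also tested when the probe by time interaction was statistically significant". It gives none for the treatment effect.

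**The concern.** None of the four outputs is the high-minus-low difference in walk change at V4. In the change-score model a non-significant interaction leads to a single effect averaged over 9 and 18 sessions. A significant interaction leaves it open which treatment comparison is the result. The raw-data interaction is a valid global test of differential change, but it gives no 6-week estimate. The raw-data main effect averages in a visit before randomisation.

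If benefit builds with the number of sessions, the average lies below the 6-week effect, and a reader cannot set the reported figure against the 50 m planned for 6 weeks. The rule also lets a non-significant interaction stand in for equal effects at the two visits, which 16 per group is poorly placed to support.

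**Working it through.** **Inputs from the documents.** 16 per group, difference 50 m and SD of change 48.69 m (protocol section 8.0); V3 at 3 weeks and V4 at 6 weeks (protocol section 5.0).

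**Assumptions.** Two-sided 0.05 (the SAP states 0.05 only for the probe comparison), complete data, the same SD at V3 and V4, a V4 effect of 50 m, a V3 effect of 25, 40 or 50 m, and a correlation ρ between the V3 and V4 changes of 0.5, 0.7 or 0.9. The documents give neither the V3 effect nor ρ.

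**Step 1: the plan's own figure.** Standard error = 48.69 × √(2/16) = 17.21 m. Noncentrality = 50/17.21 = 2.90. With 30 df and critical t = 2.042, power is 0.8025, which reproduces the stated 0.802. This is the power of the V4 contrast in every scenario below.

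**Step 2: the averaged effect.** Its target is (V3 effect + V4 effect)/2. The SD of a patient's mean change is 48.69 × √((1+ρ)/2) = 42.17 / 44.89 / 47.46 m for ρ = 0.5 / 0.7 / 0.9.

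**Step 3: the interaction.** Its target is V4 effect − V3 effect. The SD of a patient's V4−V3 difference is 48.69 × √(2(1−ρ)) = 48.69 / 37.72 / 21.77 m.

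Each triple is for ρ = 0.5 / 0.7 / 0.9:

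| V3 effect | Averaged effect | Power of averaged effect | Chance interaction is significant |
|---|---|---|---|
| 25 m | 37.5 m (25% below V4) | 0.68 / 0.63 / 0.58 | 29% / 44% / 88% |
| 40 m | 45 m (10% below) | 0.83 / 0.78 / 0.74 | 9% / 11% / 24% |
| 50 m | 50 m (no bias) | 0.90 / 0.86 / 0.82 | 5% (nominal level) |

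With V3 at 25 m, the interaction would be dropped in 71% of trials at ρ = 0.5 and 56% at ρ = 0.7. In simulation, the averaged estimate among trials with a non-significant interaction still has mean 37.5 m (45.0 m when V3 is 40 m), so the interaction test does not screen out the dilution.

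**Step 4: what a non-significant interaction can show.** The observed difference between the V3 and V4 effects must exceed 2.042 × SD of the difference × √(2/16) = 35 / 27 / 16 m to be significant, which is 70% / 54% / 31% of the 50 m planning effect. A true difference of 50 / 39 / 22 m is needed for 80% power.

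**Step 5: the whole procedure, if visit-level tests followed a significant interaction.** The SAP does not state this step. The simulation (200,000 replicates per setting) takes the averaged test when the interaction is not significant, and otherwise counts significance at V3 or V4. Power is 0.76 / 0.75 / 0.79 (V3 = 25 m), 0.84 / 0.80 / 0.77 (40 m) and 0.91 / 0.87 / 0.83 (50 m). Type I error is 6.6% / 6.0% / 5.5%.

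**Step 6: the raw-data interaction as a treatment test.** Under compound symmetry, which forces ρ = 0.5, an F test on 2 and 60 df with residual SD 48.69/√2 has power 0.84, 0.77 and 0.72 for V3 effects of 50, 40 and 25 m.

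**The case against.** The strongest reply is that the loss of power is small and may be a gain. The figures of 0.58 to 0.68 apply only if the averaged test is always the one reported. At ρ = 0.9 with V3 at 25 m it would be reported in only about 12% of trials. With visit-level tests after a significant interaction, the procedure loses at most about 6 points against 0.80. If the effect is constant, the average gains 2 to 10 points. **This stands**, and the case should not rest on power. The qualification is that those follow-up tests are not in the SAP and would take type I error slightly above 5%.

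The average over treatment is also a legitimate target: outcomes are measured at both visits, and a sizing statement does not designate a primary analysis. **This stands in part.** The SAP does not declare the average as its target. It arrives there only when a test with little power fails to reject, and the protocol's 50 m benchmark belongs to 6 weeks.

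The wording about equal magnitude may only describe what the coefficient represents, not claim demonstrated equality. That is a fair reading, but the model still imposes equality on the strength of a non-significant test.

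Finally, a retained interaction already contains the V3 and V4 effects, so the missing follow-up may be a drafting gap, and the raw-data interaction is a valid global test. Both are true. Neither yields a V4 estimate when the interaction is removed.

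**Conclusion.** The concern holds. The documents size the trial on the 6-week difference in walk change and then set an analysis rule that yields either an average over 3 and 6 weeks or an interaction with no stated treatment comparison. The sample size itself is not in question; it reproduces.

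The main defects are the averaged estimate and the unstated comparison, not lost power. The average is 25% too low as an estimate of the 6-week effect if the V3 effect is half the V4 effect, 10% too low if it is four-fifths, and not biased if the two are equal. The omission is certain from the text. Its practical size rests on a V3 effect and a V3-V4 correlation that the documents do not give. It is a cheap improvement, not a flaw that undermines the trial.

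**What to change.** In the change-score model for walk distance, keep the time-by-intervention term whatever its p-value. Report the high-minus-low difference at V4 with a 95% confidence interval as the main walk-distance comparison, justified by protocol section 8.0. Report the V3 difference and the V3/V4 average as secondary. Do not offer the raw-data main effect as evidence of a treatment effect.

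The SAP is written in the past tense and already remarks on the consistency of the results, so the contrast must be labelled as added and not presented as prospectively specified.

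The cost is one contrast from a model already fitted and one sentence of explanation; no new data are needed. The price is power of 0.80 for the main comparison instead of 0.82 to 0.90 if the effect is constant from 3 to 6 weeks. This covers walk distance only. The standing of the vascular outcomes, which protocol section 5.0 also treats as primary, is a separate question.
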